4.1 Eligibility Criteria

Randomized Controlled Trial. To be eligible for randomization, women must 1) be age 30-65 years; 2) have no history of hysterectomy or cervical cancer; 3) have at least 2 visits to ambulatory care within Harris Health System in the past 5 years; 4) be enrolled in a healthcare coverage or financial assistance plan accepted by Harris Health or have been enrolled in a Harris Health coverage plan in the past 12 months; 5) not have a history of cervical dysplasia in the past 3.5 years; and 6) have not had a Pap test in the past 3.5 years or Pap/HPV co-test in the past 5.5 years. A 6-month grace period is added to allow time for women to respond to opportunistic usual care strategies (i.e., in-clinic EMR-flagging and video-based patient education).

For analytical sub-aim 1 (Describe characteristics of women who under-attend for cervical cancer screening in a safety net health system), inclusion criteria are broadened to include all women who meet inclusion criteria 1-4, but not criteria 5 (i.e., women of all screening status will be included in the analysis).

Telephone Survey. To be eligible for the telephone survey, women must 1) have participated in RCT (and thus have met RCT inclusion criteria above) and 2) have been randomized to Arm 2 or 3.

Qualitative Interviews To be eligible for the qualitative interviews, women must 1) have participated in RCT (and thus have met RCT inclusion criteria above); 2) have been randomized to Arm 2 or 3; and 3) had an HR-HPV positive test result.

For COVID-19 era analytics sub-aims, inclusion criteria are broadened to include women ages 18-65 years who meet inclusion criteria 3 and 4 (i.e., we will include all women 18-65 years who have used Harris Health ambulatory care services at least twice in the past 5 years and who have a healthcare coverage plan accepted by Harris Health).

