2.2 Secondary Objectives

Analytical sub-aims of the protocol are to: 1) Describe characteristics of women who under-attend for cervical cancer screening in a safety net health system; 2) Explore patterns of detection and treatment of cervical pre-cancers across study arms; 3) Compare characteristics of screening participants across study arms.

We will also conduct a nested study within the randomized controlled trial to assess acceptability of and experiences with self-sample HPV testing among underscreened women in our safety net health system. The nested study has two components: a telephone survey and in-depth

qualitative interviews. In the remainder of the protocol these will be referred to as "Telephone Survey" and "Qualitative Interviews."

Because of the COVID-19 pandemic, we have revised some elements of the trial, as reflected throughout the protocol. One of these revisions includes expansion of analytic sub-aim 1 (above) to include monitoring of ambulatory, and more specifically, primary care utilization in addition to cervical cancer screening. The COVID-19 era sub-aims are: 1) To compare changes in cervical cancer screening and primary care utilization (overall and by face-to-face vs. telehealth modalities) among socioeconomic, racial/ethnic, and nativity subgroups in the 12-months following the COVID-19 emergency declaration; and 2) To compare the role of individual and neighborhood-level factors on cervical cancer screening and primary care utilization (overall and modality-specific) before and after the COVID-19 emergency declaration. In the remainder to the protocol, we will refer to COVID-19 era analytic sub-aims.

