COVID-19 era analytic sub-aim: 1) We will use descriptive statistics (bivariable tables and chi-square/Fisher's exact tests) to compare characteristics of women who do/do not attend for cervical cancer screening, primary care (all types), and telehealth-specific primary care. We will compare proportions at baseline (February 2020, pre-pandemic), and at 6- and 12-months post COVID-19 emergency declaration (July 2020 and February 2021). Independent multivariable Poisson regression models will be used to assess the independent association between cervical cancer screening and primary care utilization and participant characteristics.

Additional variables will be collected to meet the aims of the NIH-funded supplement (3R01MD013715-04S1) to the parent self-sampling trial: HIV status, Preventive Care Gap Score, Enrollment in MyHealth portal, History of COVID-19 diagnosis, HPV vaccination status and Risk of Admission or ED visit.

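### The COVID-19 sub-aims drop the hysterectomy and cervical cancer exclusion for the screening outcome, which dilutes absolute screening levels and can bias subgroup comparisons

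*Combined protocol and SAP*

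**What the plan says.** Section 2.2 presents the COVID-19 work as growing out of sub-aim 1: "One of these revisions includes expansion of analytic sub-aim 1 (above) to include monitoring of ambulatory, and more specifically, primary care utilization". The first COVID-19 sub-aim is "To compare changes in cervical cancer screening and primary care utilization" among subgroups defined by socioeconomic position, race/ethnicity and nativity. Section 3.4 will "compare characteristics of women who do/do not attend for cervical cancer screening, primary care (all types), and telehealth-specific primary care", compares proportions at February 2020, July 2020 and February 2021, and fits Poisson models whose covariates are not listed.

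Section 4.1 sets one population for all of this: "inclusion criteria are broadened to include women ages 18-65 years who meet inclusion criteria 3 and 4". The parenthesis that follows restates it without carving out a screening-eligible subset: "we will include all women 18-65 years who have used Harris Health ambulatory care services at least twice in the past 5 years", together with coverage.

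Criterion 2 in the same section requires that women "have no history of hysterectomy or cervical cancer". It applies to the randomized trial and to sub-aim 1, for which "inclusion criteria are broadened to include all women who meet inclusion criteria 1-4, but not criteria 5". Nothing in 2.2, 3.4 or 4.1 restores it for the COVID-19 screening outcome.

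**The concern.** The two outcomes need different denominators. Any woman enrolled in the health system can use primary care, so criteria 3 and 4 (prior visits and coverage) describe that denominator well. Cervical screening is different: a woman without a cervix cannot attend for it, and a woman treated for cervical cancer is outside routine screening. Under the population as written, both are classed with women who could have been screened and were not.

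The stated purpose is to compare screening between social and ethnic subgroups. If the share of women failing criterion 2 differs between those subgroups, part of any observed gap reflects surgical or cancer history rather than access to screening during the pandemic, and the Poisson coefficients for those characteristics would carry it as an apparent disparity.

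**Working it through.** The plan states no rate, sample size or power for these sub-aims, so there is no figure of its own to reproduce. The check sets the populations side by side and then follows the effect on the denominator.

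**Populations in section 4.1**

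| Analysis | Age | Criterion 2 | Criteria 3 and 4 | Criterion 6 (no recent test) |
|---|---|---|---|---|
| Randomized trial | 30-65 | applied | applied | applied |
| Sub-aim 1 | 30-65 | applied | applied | not applied |
| COVID-19 sub-aims | 18-65 | not applied | applied | not applied |

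**Formula.** Let s be the proportion screened among women who meet criterion 2, and h the share of the population who fail it. If those women contribute no screening, the observed proportion is p = s × (1 − h). Neither s nor h is in the documents; every value below is an assumption for illustration.

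**1. Level.** With s = 0.30:
- h = 5%: 0.30 × 0.95 = 0.285
- h = 10%: 0.30 × 0.90 = 0.270
- h = 20%: 0.30 × 0.80 = 0.240

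**2. Two subgroups with identical s and different h.** The true ratio is 1.00. The observed ratio is (1 − h_B)/(1 − h_A):

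| h_A v h_B | Arithmetic | False ratio |
|---|---|---|
| 2% v 5% | 0.95/0.98 | 0.969 |
| 5% v 10% | 0.90/0.95 | 0.947 |
| 5% v 15% | 0.85/0.95 | 0.895 |
| 10% v 20% | 0.80/0.90 | 0.889 |
| 5% v 20% | 0.80/0.95 | 0.842 |
| 10% v 25% | 0.75/0.90 | 0.833 |

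**3. Different s, same h.** With s = 0.30 v 0.20, the true difference is −10.0 points.
- h = 10%: 0.18 − 0.27 = −9.0 points
- h = 20%: 0.16 − 0.24 = −8.0 points
- The ratio is 0.667 in both cases, because (1 − h) cancels.

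**4. Change over time.** Let s halve from 0.30 to 0.15 in both subgroups, with h fixed over time. The true difference between the changes is 0.
- h = 5%: 0.285 to 0.1425, a change of −14.25 points
- h = 10%: 0.270 to 0.135, a change of −13.5 points
- h = 20%: 0.240 to 0.120, a change of −12.0 points
- False difference between absolute changes: −13.5 − (−14.25) = +0.75 points for 5% v 10%; −12.0 − (−14.25) = +2.25 points for 5% v 20%
- Relative change is 0.50 in every subgroup, so the ratio of relative changes stays 1.00.

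**5. If the outcome is up-to-date status instead.** Take 60% up to date among women meeting criterion 2, and count those failing it as not up to date.
- 5% v 10%: 0.60 × 0.95 = 0.57 and 0.60 × 0.90 = 0.54; ratio 0.947
- 5% v 20%: 0.57 and 0.60 × 0.80 = 0.48; ratio 0.842

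The criterion 2 problem is thus the same under either meaning of the outcome.

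**The case against.** The best defence is that this is a descriptive, observational addition whose first aim concerns change, and a fixed ineligible share drops out of relative change (step 4). The Poisson model works on the ratio scale, where an equal share also drops out (step 3). The documents give no share by subgroup, so neither the size nor the direction of any bias can be established from them. All of this stands, and it limits the point. It does not remove it: the plan also compares proportions at each date and models the association of screening with participant characteristics, and unequal shares do not cancel from those.

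A reader might go further and infer that recently screened women are also wrongly counted as not attending at every date, and that only women who are due belong in the denominator. The documents do not support this. Section 3.4 gives three dates but no look-back window, so a woman tested shortly before February 2020 could count as screened at baseline. Sub-aim 1 deliberately admits women whatever their screening status, and section 3.4 contrasts under-screened with up-to-date women there; on such an outcome a recently screened woman counts as a success and should stay in.

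It is equally tempting to say that, under the three-year interval in section 1.2, about two thirds of adherent women are not due in any given year. That describes a hypothetical group and quantifies no bias in any planned contrast. It also overlooks the separate co-test rule in criterion 6: "have not had a Pap test in the past 3.5 years or Pap/HPV co-test in the past 5.5 years".

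Nor should criterion 1 be reinstated on the strength of this point. It would remove women aged 18-29 and reverse a broadening that section 4.1 states on purpose, and the documents do not define a different age range for routine screening.

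**Conclusion.** The point holds for criterion 2 and for the screening outcome only. Followed as written, section 4.1 counts women with a past hysterectomy or cervical cancer as not attending for screening, while sub-aim 1 excludes them and no reason is given for the difference.

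- **Levels and absolute changes:** diluted by the factor (1 − h) whenever such women are included and contribute no screening.
- **Ratios between subgroups:** biased only if h differs. Over the assumed range the false ratio runs from 0.97 (2% v 5%) to 0.83 (10% v 25%).
- **Relative change within a subgroup:** unaffected if h is constant over the three dates.

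It would be too strong to say that the subgroup contrasts are distorted outright; that depends on shares the documents do not report. The broad population remains suitable for primary care use, and the randomized comparisons are untouched. The change is worth making because it is cheap and brings the screening analysis back into line with sub-aim 1.

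**What to change.** In sections 4.1 and 3.4, state two populations for the COVID-19 sub-aims. For primary care use, keep women aged 18-65 who meet criteria 3 and 4. For cervical screening, additionally apply criterion 2, as sub-aim 1 does. Reporting the share removed by criterion 2 in each subgroup would let readers see how much it matters.

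Separately, section 3.4 should say whether the screening outcome is attendance within a window or up-to-date status at each date. No due-only restriction should be added on the strength of this point.

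The cost is a change of wording and of the records query. Trial eligibility already requires hysterectomy and cervical cancer history at ages 30-65; the query would have to be extended to ages 18-29. The screening denominator becomes smaller by the share h, and the screening and primary care results will rest on slightly different groups of women, which the report should state.

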4.2 Exclusion Criteria

Randomized Controlled Trial Patients who self-pay will be excluded unless they were covered under a Harris Health healthcare coverage plan within the past 12 months. This is to ensure that all participants are able to receive follow-up clinical care from Harris Health System, as needed. For those with expired eligibility, expedited emergency coverage can be instituted as needed, per a process worked out with Harris Health System financial assistance leadership. Additional exclusion criteria will be assessed by chart review and at the time of attempted telephone contact. Specifically, we will exclude women who lack valid telephone contact information; are unable to communicate in English, Spanish, Vietnamese or other Asian language where translation services are available; or self-report being currently pregnant.

Telephone Survey Women who test positive for HR-HPV and require clinical follow-up are not eligible for the survey.

Qualitative Interviews Women who test negative for HR-HPV are not eligible for the qualitative interviews.

4.3 Vulnerable Populations

4.3.1 Children

Children will not be enrolled in this study.

4.3.2 Pregnant women

Pregnant women will not be enrolled in this study.

4.3.3 Cognitively Impaired

Cognitively impaired subjects will not be enrolled in this study.

4.4 Recruitment Methods

5 Randomized Controlled Trial. Eligible women will be identified monthly through a query of the EMR database. Data will be extracted and transferred to OnCore (Forte Research Systems, Madison, WI) for randomization, storage, and data management. A computer-generated permuted block randomization scheme will be used to randomly assign individuals to the three trial arms with a 1:1:1 ratio using participants' medical record number. Randomized women will be contacted by telephone. We have requested a waiver of consent for the data extraction and phone calls. Patients who are not reached will be contacted on 3 different days at 3 different times before being classified as unreachable.

The patient navigators performing the calls will undergo training in Human Subjects research and arm-specific procedures. The language used by the patient navigators is standard to non-research patient navigation, and is designed in a way that makes it clear to patients that they are free to make their decisions of whether or not they would like to participate in screening.

For patients in Arm 2 and 3, we will use an Introduction Letter and Research Information Sheet which contains all the information usually contained in a consent form rather than a formal informed consent form. The Introduction Letter indicates that, as an alternative to a Pap test, participants can complete and return the enclosed self-sampling kit. It clearly states that the self-sampling kit is part of a research study conducted by Baylor College of Medicine. It also asks participants to closely read the attached Research Information Sheet. The Research Information Sheet describes the study's purpose, procedures, voluntary participation, risks and benefits, and protection of privacy and confidentiality. Both documents The Research Information Sheet states that participation is voluntary and that choosing not to participate does not result in any lost rights or benefits as a Harris Health patient. Potential participants are also informed that they may decide to stop taking part at any time and that doing so will not change the health care that they receive now or in the future. The letter provides a number to call to revoke authorization for review of medical record data. It also includes a number to call with questions and concerns and to report an injury or other adverse event

We request not to require signing the form, because we fear that it will introduce significant bias into our research. Instead we have included language in both the letter and the information sheet that makes it clear to participants that their completion and return of the self-sampling kit indicates their consent to participate.

Finally, none of the subjects are being compensated for their participation in this study, so there is no financial influence in participant's decision to take part in the study.

The introductory letter and research information sheet are available in English and Spanish. Both versions are attached in Section S.

Telephone Survey Women who are randomly selected to participate in the telephone survey and women who are selected to participate in the qualitative interviews will be contacted by telephone by a trained, bilingual research assistant and invited to participate in the survey. The informed consent will be read to participants, emphasizing voluntary nature of the study and that participation will not affect their participation in the larger RCT or their ability to obtain healthcare services at Harris Health. Women will be given the opportunity to ask questions. After doing so, they will be asked to verbally indicate whether they agree to participate in the survey/interview.

Consent and Enrollment of Vietnamese-speaking Subjects See attachment, file name: "209230 - Baylor College of Medicine_COA" for certificate of translation of Vietnamese-language materials. See attachment, file name: "Consent and Enrollment of Vietnamese-speaking Subjects".

6 STUDY ASSESSMENTS AND PROCEDURES

6.1 Schedule of Activities (SoA)

Arm 1: Telephone recall (control). Participants will receive a scripted telephone recall from a trained patient navigator (PN) on behalf of Harris Health.

Arm 2 Telephone recall with mailed HPV self-sampling kit.

Arm 3: Telephone recall with mailed HPV self-sampling kit and patient navigation (intervention plus). Participants in this arm will receive the same scripted telephone recall and mailed self-sampling kit as in Arm 2. Within 3-5 days of the kits mail-out, participants will receive a telephone call from the PN. The PN will provide one-on-one education involving three overlapping domains: 1) information on the nature and purpose of cervical cancer screening and the causative role of HR-HPV; 2) the ability to complete screening through a clinic-based Pap test or through self-sample HPV testing using the kit; and 3) instruction on how to use and return the completed kit. Participants who indicate preference to undergo a Pap test will be assisted with scheduling an appointment with a Harris Health provider.

Participants who indicated intent to self-sample but whose kit is not received by the lab within 3 weeks of mail-out will receive up to 3 telephone reminders and a letter if unreachable by phone.

Arm 3 will also receive information on telehealth options available for Harris Health patients and will be given the phone number for help accessing telehealth. Mailed self-sample HPV testing (Arms 2 and 3) HPV self-sampling kits will include an introductory letter, research information sheet, self-sampling kit, instructional brochure, and a labeled, pre-paid envelope addressed to the Harris Health central offices.

Test results will be sent via Harris Health secure transmission to co-investigator [name], the study coordinator, and the PN team. Notification of test results and referral for clinical follow-up: HR-HPV positive test results will be communicated on a weekly basis to co-investigator [name]. [name] will be responsible for referring HR-HPV positive women to clinical follow-up. Notification to participants of both negative and positive results will be conducted by the PNs, who will contact participants by telephone within 10 days of the laboratory's receipt of the sample.

Participants who are unreachable after 3 telephone attempts on different days/times will be mailed their results by certified mail. Results will be reported as follows: HR-HPV negative women will be told that no high-risk HPV strains were found in their sample. However, since self-sampling is not currently approved for primary screening, women will be advised to attend for clinic-based screening within the next 12 months.

Women who test positive for HR-HPV but negative for 16/18/45 will be referred by [name] to clinic-based screening (Pap/HR-HPV co-testing). They will be asked to make an appointment with their healthcare provider and given clinic contact information. Women who test positive for HR 16/18 will be referred to colposcopy. As is standard practice at Harris Health when screening abnormalities are encountered, women requiring follow-up Pap test screening or colposcopy who have not made an appointment within 30 days of test result notification will receive a telephone call from a PN who will assist them with scheduling an appointment. Inadequate: Women whose samples were inadequate (due to unsatisfactory sampling or kit returned after >30 days) will be advised to attend for clinic-based screening or mailed a new kit. **Ascertainment of Outcomes**
Primary outcome. The primary outcome is primary screening participation, defined as completion and return of a mailed self-sample HPV testing kit that is tested in the lab or attendance for clinic-based screening within 6 months of randomization. Receipt of mailed self-sample HPV testing kits will be ascertained by reviewing lab records. Attendance for clinic-based screening will be ascertained by the study coordinator based on review of the Harris Health EMR. Primary screening participation will be dichotomously categorized as screened/unscreened. Secondary outcomes are screening tests results (positive, negative, or inadequate) and completion of clinical follow-up among women with an abnormal screening test result (attended, did not attend).

Screening test results will be ascertained within 6 months of randomization. Pap/HR-HPV co-testing results will be ascertained by EMR review. Self-sample HR-HPV test results will be based on laboratory reports. Completion of clinical follow-up will be ascertained by EMR review within 6 months of the date of the screening test result. Completion of clinical follow-up is defined as attendance for colposcopy among participants who had a positive test by clinic-based screening and attendance for colposcopy or subsequent clinic-based screening among those who had a positive test by self-sampling. Additional exploratory outcomes (sub-aim 2) are detection and treatment of cervical precancers (i.e., histologically-confirmed cervical intraepithelial neoplasia grade II or greater [CIN2+]). Precancers will be ascertained by EMR review within 6 months of abnormal screening results and treatment as per ASCCP guidelines will be ascertained within 6 months of the date of diagnosis. Completion of primary care appointments will be ascertained at 6 months, including telehealth appointments.

Study Calendar A – Editable Example				
	Study Timepoints			
	Screening	Telephone survey	Qualitative Interview	Outcomes chart review
Informed Consent	X			
Demographics	X			
Clinical history	X			
Questionnaire		X	X	X
Intervention: Data collection, questionnaires		X	X	X
Adverse Events Reporting	X	X	X	X

